6.8 Subject Diary

A diary will be handed out to the subject at Visit 1, Visit 2, and Visit 3.

- Every time gel is applied, the subject must document the time and date of application. This includes gel applied at the clinic site
- Pain intensity and pain relief will both be assessed by the subjects every 2 hours ± 30 minutes (after starting study drug) until the subject goes to bed on the evening of Day 1. The same assessment and recording frequency will also be followed starting with the first dose on Day 5. On Day 1 and Day 5 where an assessment time point coincides with a dosing time point, the assessment of pain intensity and pain relief should be made prior to the dose. For all other time periods, pain intensity and pain relief will be assessed and recorded immediately prior to each study drug application.
- Every time rescue medication is taken (not allowed within 6 hours of Study Visits and within 12 hours of Study Visit 3), the subject must document:
 - Time and date of rescue medication
 - Number of tablets taken
 - Reason for use of rescue medication
 - $\circ\,$ Pain intensity and pain relief immediately prior to each dose of rescue medication

The Investigator or designee will ensure that all diary entries completed by the subject are legible. The Investigator will review the diary at each clinic visit. The diary handed out to subjects on Visit 1, Visit 2, and Visit 3 will be collected by the Investigator or designee at Visit 2, Visit 3, and Visit 4 (Day 8±1) respectively.

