12.2.6 Secondary Analysis(es)

Secondary outcome measures (endpoints) include:

- Change from baseline of POM on VAS on Days 3 and 8 respectively
- Tenderness measured by pressure algometry on Days 3, 5 and 8 (change from baseline and difference between the measurement in injured area and contralateral area)
- Change from baseline Ankle Joint Function (Karlsson Scoring Scale) on Days 3, 5 and 8
- Circumference measurement of swelling (change from baseline in circumference of affected ankle and comparison to non- affected ankle by Figure of Eight method on Days 3, 5 and 8)
- Pain Intensity and Pain Relief
 - Sum of Pain Intensity Difference (SPID) From hours 0 24 post first dose (corresponding to Day 1) and from hours 96 120 post first dose (corresponding to Day 5)
 - Total Pain Relief (TOTPAR) From hours 0 24 post first dose (corresponding to Day 1) and from hours 96 120 post first dose (corresponding to Day 5)

TOTPAR and SPID will be calculated as weighted sums of the Pain Relief Score and Pain Intensity Difference at each timepoint respectively:

 $TOTPAR = \Sigma R_t^x (time_t - time_{t-1})$

Where R_t = the pain relief score at time t and time t = time in hours post first dose

 $SPID_t = \Sigma PID_t (time_t - time_{t-1})(h)$

Where PI is pain intensity

- Use of rescue medication, for ankle sprain and overall
 - Total number of tablets used
 - Total number of days on which rescue medication was used

Figures will show the time course of outcomes by treatment group for key quantitative outcomes.

For POM, Karlsson score, tenderness, swelling and diary assessments (SPID and TOTPAR), an ANCOVA model including treatment group and center as main effects, and the baseline value as covariate (those outcomes for which there is a baseline) will be used for analysis, with the treatment difference and 95% confidence interval (two-sided) presented for each assessment.

Use of rescue medication (number of tablets and days used) will be compared between treatments using the CHM method (modridit scores) stratified by center, with the median treatment differences and 95% confidence intervals (2-sided) presented using Hodges-Lehmann estimation.

These secondary endpoints will be analyzed using the per protocol and mITT populations.

GlaxoSmithKline Consumer Healthcare Confidential Template Version Effective: 18-May-18 (CCR #11475) Page **54** of **64**

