## 3 Considerations for data analyses and Data Handling Conventions

## 3.1 Baseline Definition

For all endpoints the baseline value will be the latest pre-dose assessment with a non-missing value. Unless otherwise stated, if baseline data is missing no derivation will be performed and will be set to missing.

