#### 4.5.2 Secondary Efficacy Variables

The secondary efficacy analyses will be performed and also be listed on mITT and PP population.

- Change from baseline of POM (CRF page: Pain on Movement; VAS score will be obtained from VASSCRL) on VAS on days 3 and 8 respectively (PPD).
- Tenderness measured by pressure algometry on days 3, 5 and 8 which will be analysed using change from baseline and difference between the measurement in injured area (CRF page: Tenderness; measurement for study ankle : QS\_INJA) and contralateral area (CRF page: Tenderness; measurement for study ankle : QS\_CLTA) (PPD)...
- Change from baseline Ankle Joint Function (Karlsson Scoring Scale; CRF page: Ankle Joint Function: Variable : Total Score KSSTS) on days 3, 5 and 8 (PPD)...
- Circumference measurement of swelling on days 3, 5 and 8 which will be analysed using change from baseline in circumference of affected ankle and comparison to non-affected ankle by Figure of Eight method (CRF Page:Ankle swelling; Variables: FOEMINSC and FOEMCASC respectively.) (PPD)...

GlaxoSmithKline Consumer Healthcare Confidential

Page 21 of 36

211206

Statistical Reporting and Analysis plan Draft V2.0 20JAN2021

- Pain Intensity and Pain Relief (CRF Page: Subject Diary(Day 1/5); variables will used to calculate the Pain Intensity and Pain Relief are DPI and DPR respectively for each timepoint (DSTMPT))
- Pain Intensity (**PPD**)..
  - Pain intensity will be analysed based on the Sum of Pain Intensity Difference (SPID). SPID is defined as from 0 -24 hours post first dose corresponding to day 1 and from 0-24 hours post first dose corresponding to day 5.
  - SPIDt=>PIDt(timet-timet-1)(h), where, PIDt=pain intensity score (DPI from CRF page corresponding to day); timet=time in hours post first dose
  - Pain Relief (**PPD**)...:
    - Pain relief will be analysed based on the Total Pain Relief (TOTPAR). TOTPAR is defined as from 0-24 hours post first dose corresponding to day 1 and from 0-24 hours post first dose corresponding to day 5.
    - TOTPAR=∑Rt(timet-timet-1), whert e Rt=pain relief score (DPR from CRF page corresponding to day)

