## 4.6 Analysis of Secondary Objectives

## 4.6.1 Efficacy (Secondary)

All the secondary endpoints POM at day 3 and 8, Karlsson score, tenderness, swelling and diary assessments (SPID and TOTPAR) will be analyzed using an ANCOVA model with treatment and center as fixed effect, baseline assessment for the corresponding endpoints as covariate. Treatment differences and two-sided 95% CI will be presented.

The secondary efficacy analyses will be performed and also be listed on mITT and PP population.

- Change from baseline of POM (CRF page: Pain on Movement; VAS score will be obtained from VASSCRL) on VAS on days 3 and 8 respectively (PPD).
- Tenderness measured by pressure algometry on days 3, 5 and 8 which will be analysed using change from baseline and difference between the measurement in injured area (CRF page: Tenderness; measurement for study ankle : QS\_INJA) and contralateral area (CRF page: Tenderness; measurement for study ankle : QS\_CLTA) (**PPD**)...
- Change from baseline Ankle Joint Function (Karlsson Scoring Scale; CRF page: Ankle Joint Function: Variable : Total Score KSSTS) on days 3, 5 and 8 (PPD)...
- Circumference measurement of swelling on days 3, 5 8 which will be analysed using change from baseline in circumference of affected ankle and comparison to non-affected ankle by Figure of Eight method (CRF Page:Ankle swelling; Variables: FOEMINSC and FOEMCASC respectively.) (PPD ;)..
- Pain Intensity and Pain Relief (CRF Page: Subject Diary(Day 1/5) ; variables will used to calculate the Pain Intensity and Pain Relief are DPI and DPR respectively for each timepoint (DSTMPT))
- Pain Intensity (PPD
  - Pain intensity will be analysed based on the Sum of Pain Intensity Difference (SPID). SPID is defined as from 0 -24 hours post first dose corresponding to day 1 and from 0-24 hours post first dose corresponding to day 5.
  - SPIDt=>PIDt(timet-timet-1)(h), where, PIDt=pain intensity score (DPI from CRF page corresponding to day); timet=time in hours post first dose

GlaxoSmithKline Consumer Healthcare Confidential

Page 23 of 36

211206

Statistical Reporting and Analysis plan Draft V2.0 20JAN2021

- Pain Relief (**PPD** 
  - Pain relief will be analysed based on the Total Pain Relief (TOTPAR). TOTPAR is defined as from 0-24 hours post first dose corresponding to day 1 and from 0-24 hours post first dose corresponding to day 5.

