#### 211206

Statistical Reporting and Analysis plan Draft V2.0 20JAN2021

- 3. Compliance-Sensitivity analysis: Subjects with good compliance has been added in analysis to check if there is any change in variability in POM.
- 4. There will be additional sensitivity analysis conducted for COVID 19 affected subjects for which protocol will not be updated.
- 5. The definition of Per Protocol Population has been modified in the RAP.
- 6. The protocol deviation criterion of compliance has been modified.

Any changes from the originally planned statistical analysis specified in the protocol are outlined in Table 3.

 Table 3
 Changes to Protocol Defined Analysis Plan

| Protocol                                   | Reporting & Analysis Plan    |  |
|--|------------------------------|--|
| Statistical
Analysis
section         | Statistical
Analysis Plan | Rationale for Changes  |
| • Section
12,
Subsection
12.2.6   | • Section 4.4.3              | • Rescue medication can be clearly analysed defining time to event data.   |
| • Section
12,
Subsection
12.2.6   | • Section 4.5.2              | • Sine the "Day 5", 96 hour is not actual 96th hour with respect to first treatment start time, so as per clinical consideration it's start of Day 5 and consider as 0 hour of Day 5.  |
| • New addition                             | • Section 4.5.1              | • Compliance Sensitivity Analysis: This analysis has
been done to check if there is any change in variability
in POM based on good compliance  |
| • New addition                             | • Section 4.7.5              | • COVID analysis: As the pandemic started at the time of recruitment, as per regulatory requirement sensitivity analysis is planned for COVID patients, if any.  |
| • Section
12.2.
Subsection
12.2.1 | • Section 4.2.3              | • It was observed that most of the subjects has $50\% \le$ weight compliance $\le 80\%$ . However these subjects has full and proper Pain on Movement measurements available. Based on these observations it has been decided to re look on the definition of PP Population. |
| • New addition                             | • Section 4.2.2              | • For overdosed subjects the PP exclusion reason was
updated as "Other deviation-weight
compliance >=143% or application   |

GlaxoSmithKline Consumer Healthcare Confidential

Page 28 of 36

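### The SAP defines SPID's pain intensity difference as the raw diary score, so the endpoint as written sums pain and not change in pain

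*SAP*

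**What the plan says.** Protocol 12.2.6 says that TOTPAR and SPID are "weighted sums of the Pain Relief Score and Pain Intensity Difference at each timepoint respectively", each term multiplied by the time since the previous assessment. Its legend identifies PI as pain intensity but never writes PID_t out as a subtraction, so it gives neither the reference value nor the sign.

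SAP 4.5.2, repeated in 4.6.1, still calls the endpoint the sum of pain intensity difference, but defines PID_t as "pain intensity score (DPI from CRF page corresponding to day". DPI is the diary score. Protocol 9.2.5 puts it on a scale from 0 (no pain) to 3 (severe). Neither SAP section contains a baseline term.

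On baseline, SAP 3.1 says that "the baseline value will be the latest pre-dose assessment with a non-missing value". Protocol 9.2.5 places the diary baseline just before the first dose, and Protocol 8.1.6 has it recorded in the CRF at Visit 1. SAP 4.6.1 analyses SPID by ANCOVA with treatment, center and "baseline assessment for the corresponding endpoints as covariate".

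SAP section 5 states that "Any changes from the originally planned statistical analysis specified in the protocol are outlined in Table 3". For pain intensity and relief the only change listed there is the Day 5 window, whose start the SAP will "consider as 0 hour of Day 5". SAP 4.5.2 accordingly takes the second SPID "from 0-24 hours post first dose corresponding to day 5".

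**The concern.** A sum of differences and a sum of scores are different quantities. For TOTPAR, summing the raw relief score is correct. The SAP uses the parallel wording for SPID, where it is wrong. A programmer who follows the printed definition will report a time-weighted total of pain under the name SPID. High values would then be bad, while high TOTPAR values are good, and nothing in the SAP warns of this.

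The missing term also means that the SAP never says which baseline is to be subtracted for Day 5. The Day 5 clock restarts at hour 0 after a first dose. Protocol 6.8 says that when an assessment on Day 1 or Day 5 coincides with a dose, "the assessment of pain intensity and pain relief should be made prior to the dose". A rule that takes the latest pre-dose value could therefore be read as pointing to the Day 5 morning score. Used as the ANCOVA covariate, that score would adjust for a value measured after about four days of treatment.

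At stake are the meaning of the reported SPID means and the direction in which the treatment difference is read. The primary non-inferiority test is not at stake.

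**Working it through.** The documents give no numerical figure for SPID, so there is none to reproduce. The check compares the two definitions on simple diary profiles and then follows them through the ANCOVA.

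**Inputs from the documents.** Scores run from 0 to 3 (Protocol 9.2.5). Assessments are every 2 hours until bedtime on Day 1, with the same frequency on Day 5 (Protocol 6.8 and 9.2.5). Each weight is the time since the previous assessment (Protocol 12.2.6).

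**Assumptions for illustration.** Baseline b = 3 and six post-baseline entries, so the recorded time is T = 6 × 2 = 12 h.

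**Formulas.**
- As written in the SAP: S = Σ PI_t × (time_t − time_{t−1}).
- Baseline minus current: Σ (b − PI_t) × (time_t − time_{t−1}) = b × T − S = 36 − S.
- Current minus baseline: S − 36.

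**Day 1 profiles**

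| Profile | As written | Baseline − current | Current − baseline |
|---|---|---|---|
| Improver (3,2,2,1,1,1) | 2 × 10 = 20 | 2 × 8 = 16 | −16 |
| Severe pain, no relief (3 throughout) | 2 × 18 = 36 | 0 | 0 |
| Complete relief (0 throughout) | 0 | 2 × 18 = 36 | −36 |

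**Day 5 window, Day 1 score of 3**

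| Day 5 profile | As written | SPID from Day 1 score | SPID from Day 5 pre-dose score |
|---|---|---|---|
| Steady at 1 | 2 × 6 × 1 = 12 | 2 × 6 × (3 − 1) = 24 | 2 × 6 × (1 − 1) = 0 |
| Steady at 3 | 2 × 6 × 3 = 36 | 0 | 0 |

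If the Day 5 morning score were taken as baseline, the subject who improved and the subject who did not would both score 0.

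**Effect on the treatment comparison.** If T is the same for everyone, b × T is a fixed multiple of b. With the Day 1 score b in the model as covariate, that term is absorbed completely. The treatment coefficient for b × T − S is then exactly minus the coefficient for S, with the same standard error. For S − b × T it equals the coefficient for S. A check on invented data (240 subjects, 8 centers, equal recording time, ANCOVA with treatment, center and Day 1 baseline) gave −3.441 as written, +3.441 for baseline minus current and −3.441 for current minus baseline, with SE 0.900 in all three. These values show the algebra only and do not estimate anything in this trial.

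If T differs between subjects, b × T is no longer a multiple of b and is not absorbed, so the two analyses are not mirror images. Unequal T is possible here because diary entries stop at bedtime and missing entries are not imputed (SAP 4.5.3). Both quantities depend on the hours recorded, so this does not show that one is more variable than the other.

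**The case against.** The strongest reply is that this is an incomplete legend and not a changed analysis. The protocol never prints PID_t as a subtraction, so the SAP conflicts with the term pain intensity difference and not with a formula. The SAP keeps the name SPID, and the reference to DPI can be read as a pointer to the source variable, like the CRF variable names in the neighbouring bullets. The sample code is not readable in the public copy, so what would be programmed cannot be seen. It may well be a drafting slip. Even so, the SAP's is the only readable definition of PID_t, it appears twice, and following it sums raw scores.

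A second reply is that SAP 3.1 together with Protocol 9.2.5 already supplies a baseline, the score before the first dose on Day 1, and that the restarted Day 5 clock says nothing about baseline. That is the better reading, and the Day 5 zero scores above arise only under the other one. But the wording of the Day 5 window leaves the other reading available, and naming the baseline costs nothing.

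A third is that running opposite to TOTPAR proves no error, since current minus baseline would do the same. That stands: the sign is a convention, and the documents do not state it. The absence of any subtraction is the error.

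**Conclusion.** The point holds and is minor. As printed, the SAP's SPID is a time-weighted sum of pain, contrary to the difference that Protocol 12.2.6 calls for, and section 5 does not declare the change. Group means would be on the wrong scale: in the 12-hour illustration, 36 against 0 for unrelieved severe pain. The treatment difference keeps its size and standard error provided that recording time is equal across subjects and the Day 1 score is the covariate. Its sign flips only if the intended difference is baseline minus current. With unequal recording time the effect on the estimate is not established in either direction. No bias between arms is claimed. The primary analysis of pain on movement at Day 5, on which study success rests, is unaffected. Confidence is high for the printed wording. The profiles are assumed, and the code that would be run is not visible.

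**What to change.** In SAP 4.5.2 and 4.6.1, define PID_t = PI_baseline − PI_t, so that SPID = Σ (PI_baseline − PI_t) × (time_t − time_{t−1}), and state that higher is better, as for TOTPAR. Name the Day 1 pre-dose score (Protocol 8.1.6 and 9.2.5) as PI_baseline and as the ANCOVA covariate for both the Day 1 and the Day 5 windows. If a sum of raw pain was in fact intended, declare it in section 5 and rename the endpoint.

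The cost is a one-line definition in two SAP sections. No new data are needed, because baseline pain intensity is already recorded at Visit 1. SAP 2.2 places RAP finalization before unblinding, so the definition should be settled at that step.

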#### 4.5.3 Handling of Missing Values/Censoring/Discontinuations

As a part of missing data analysis a Multiple Imputation (MI) simulation method for imputing missing data will be conducted on ANCOVA analysis for the primary efficacy endpoints on the ITT population. This will help to assess the impact of missing data on the primary analysis.

Subjects who withdraw from the study prematurely will also be included in the statistical analyses up to the point of discontinuation.

The SAS procedure MI will be used and the details of MI procedure will be stated in the dataset specification document. If the data is monotone missing, an imputation model with regression baseline parameters will be applied, otherwise Markov Chain Monte Carlo(MCMC) will be applied. All variables included in the analysis model which are used in the primary model will be used for imputation andvalues at day 3 for the primary endpoint (For Day 5) will be included in the imputation model. To reduce the sampling variability from the imputation process, 50 datasets will be generated.

In the estimation step, separate analysis will be performed using the model mentioned for the primary endpoint statistical analysis Section 4.5.1.2.

After the completion of the estimation step SAS procedure MIANALYZE will be used to pool the estimates.

Refer APPENDIX 4 for sample SAS codes.

GlaxoSmithKline Consumer Healthcare Confidential

Page 22 of 36

No imputation is planned for missing diary card pain intensity and relief assessments.

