9.2.2 Pain on Movement

The investigator will perform a manipulation of the ankle (i.e., movement) (described below), and the pain assessment will be done by the subject. These will occur at the study center on Days 1, 3, 5 and 8 (\pm 1) (Visits 1–4) using a 100 mm VAS.

The manipulation will be performed as follows:

The subject is asked to lie down on an even horizontal surface. The investigator gently lifts the leg and holds it up in the air at an angle of approximately 45° . While holding the leg with one hand, the investigator performs a gentle inversion (i.e., supination) of the foot of the injured ankle to reach an angle of approx. 30° .

The extent of ankle pain is evaluated by the subject in answer to the question:

"How would you describe your ankle pain right now?"

The pain-on-movement is registered by the subject by drawing a perpendicular line on the 100 mm VAS scale with anchors at 0 = "no pain" and 100 = "extreme pain".

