#### 4.5.1.2 Statistical Hypothesis, Model, and Method of Analysis

The hypothesis of the study is stated below:

H0: The Diclofenac 2.32% DDEA Gel administered BID is inferior to Diclofenac1.16% DDEA gel administered QID.

 $\mu_T \text{-} \mu_S \geq \delta$ 

Where,  $\mu_S$  is the mean for a standard therapy (Diclofenac 1.16% DDEA Gel administered QID) and  $\mu$ T is the mean for test therapy (Diclofenac 2.32% DDEA Gel administered BID).  $\delta$  is the non-inferiority margin of 13 mm.

H1: Diclofenac 2.32% DDEA Gel administered BID is non-inferior to Diclofenac 1.16% DDEA gel administered QID.

 $\mu_T \text{ - } \mu_s < \delta$ 

 $\delta = 13 \text{mm}$ 

The primary efficacy analysis will be performed on PP population without imputation of missing data. The primary endpoint (Change from baseline in POM ) will be analysed using

GlaxoSmithKline Consumer Healthcare Confidential

Page **19** of **36** 

211206

Statistical Reporting and Analysis plan Draft V2.0 20JAN2021

Analysis of Covariance (ANCOVA) model with treatment and center as factors and baseline POM as covariate.

Diclofenac 2.32% DDEA Gel administered BID will be declared non-inferior to Diclofenac 1.16% DDEA gel administered QID if the upper limit of the two-sided 95% confidence interval of the difference between their mean changes from baseline VAS POM responses is less than the established margin of 13 mm.

Refer sample SAS code in APPENDIX 4.

Assumptions of normality and homogeneity of variances in the ANCOVA model will be evaluated after study un-blinding. If violations are observed then the following will be performed as a post-hoc sensitivity analysis and results will be compared with primary analysis results:

- 1. Suitable data transformations will be tried to achieve the assumptions.
- 2. If suitable transformations cannot be found, then the non-parametric Van Elteren tests will be performed using center as strata. Two sided 95% CI and p value will be presented.

POM by 100 mm VAS analogue scale (CRF page: Pain on Movement ; variable VASSCRL)will be summarized over time (**PPD**) using mITT population. Also POM by 100 mmVAS analogue scale will be summerarized over time by center using mITT population (**PPD**). Above tables (**PPD**) will be repeated for the PP population. POM by 100 mm VAS analogue scale for COVID 19 patients if any will be summarized in **PPD** using mITT population.

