#### 4.5.1.3 Supportive Analyses

To assess the treatment-by-center interaction an additional analysis will be performed for the primary endpoint on mITT population as following, where change from baseline on POM will be analysed using ANCOVA model with treatment, center as fixed factor, baseline POM as covariate and treatment-by-center as interaction (PPD)
 If there is evidence of an significant interaction (p<0.05) effect, then the primary endpoint outcome will also be summarized by center for further investigation and assessment.

GlaxoSmithKline Consumer Healthcare Confidential

Page 20 of 36

Reference SAS code is given in APPENDIX 4:

- 2. Sensitivity analysis will be perfomed on POM for compliance category -good. For good category greater than or equal to 80% compliance will be considered for both in application and amount of gel used for this sensitivity analysis. The sensitivity analysis for the primary endpoint will be dispayed in the tables (**PPD**).
- 3. The primary efficacy endpoint will be analyzed using ANCOVA model on ITT population using imputed data.
- 4. The Change from baseline on POM will be analyzed using Mixed Model Repeated Measure (MMRM) with multiple imputation (day 3,5,8) model with treatment, center as fixed factor, baseline POM as covariate and visit as repeated measure; using ITT population.
- 5. Same as above mentioned point 3 without imputed data, ie, observed data.
- 6. Same as above point 3 using PP population.
- 7. Same as above point 4 using PP population.

Early discontinued subjects data due to any reason- will be analyzed in this section using imputation.

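### The supportive multiple-imputation ANCOVA predicts a missing Day 5 pain on movement (POM) from Day 3 and does not name the Day 8 value; adding it is a free, small improvement

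*SAP*

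**What the plan says.** SAP 4.5.3 describes the multiple imputation for the ANCOVA of the primary endpoint in the ITT population, which is item 3 of SAP 4.5.1.3. On the predictors it says "All variables included in the analysis model which are used in the primary model will be used for imputation". The primary ANCOVA in SAP 4.5.1.2 contains treatment, centre and baseline POM. The only post-baseline predictor added is the value "at day 3 for the primary endpoint (For Day 5) will be included in the imputation model".

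The method is regression if the missing pattern is monotone; "otherwise Markov Chain Monte Carlo(MCMC) will be applied". Fifty datasets are generated. The remaining "details of MI procedure will be stated in the dataset specification document", and the sample code in Appendix 4 is not visible in the public text.

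Day 8 POM is collected. Protocol 9.2.2 says of the POM assessments: "These will occur at the study center on Days 1, 3, 5 and 8". The SAP also uses Day 8 in another supportive analysis: item 4 of 4.5.1.3 is a repeated-measures model "with multiple imputation (day 3,5,8) model with treatment, center as fixed factor, baseline POM as covariate and visit as repeated measure", and item 7 repeats it in the per-protocol population.

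The primary analysis does not depend on any of this: "The primary efficacy analysis will be performed on PP population without imputation of missing data" (SAP 4.5.1.2).

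**The concern.** A subject who attends Visits 2 and 4 but not Visit 3 has a POM value on either side of the missing one. The model in 4.5.3 uses only the earlier value, so the imputed Day 5 value carries more noise than it needs to.

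The second issue is the missing-at-random assumption. Without Day 8, the imputation assumes that skipping Visit 3 is unrelated to Day 5 pain once treatment, centre, baseline and Day 3 are known. If people who recover quickly are the ones who skip, that assumption fails in a way the observed Day 8 value could correct. The SAP gives this imputation the job of showing how missing data affect the primary result, so it should use the measured information relevant to that question.

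The plan also leaves a link unstated. A subject with Day 5 missing and Day 8 observed is monotone if Day 8 is outside the imputation set and non-monotone if it is inside. The choice between regression and MCMC therefore depends on whether items 3 and 4 share one imputation run, and the SAP does not say.

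**Working it through.** **Inputs from the documents.** SD 22 mm, margin 13 mm, allowed true difference 5 mm in favour of the 1.16% gel, two-sided 95% CI, 120 per arm for 80% power, about 300 randomised (150 per arm), 240 evaluable (SAP 1.4; Protocol 12.1).

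**Inputs not in the documents, so assumed.** The correlations between POM at Days 3, 5 and 8 (r35, r58, r38, after adjustment for the model terms), and the fraction m of subjects with Day 5 missing but Day 8 observed. I take m from 2% to 20%. The upper end equals the whole planned non-evaluable share, 1 − 240/300 = 20%.

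**Step 1: the plan's own figure.** n per arm = 2 × 22² × (1.960 + 0.842)² / (13 − 5)² ≈ 118.7, so 119. Power at 120 per arm is 80.4%. The stated 120 reproduces; no stated figure is in dispute.

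**Step 2: what Day 8 adds for one missing value.** With Day 3 only, R² = r35². With Days 3 and 8, R² = (r35² + r58² − 2·r35·r58·r38) / (1 − r38²).

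| r35, r58, r38 | R², Day 3 only | R², Days 3 and 8 | Residual variance ratio |
|---|---|---|---|
| 0.6, 0.6, 0.45 | 0.36 | 0.396/0.7975 = 0.497 | 0.503/0.64 = 0.79 |
| 0.6, 0.7, 0.5 | 0.36 | 0.43/0.75 = 0.573 | 0.427/0.64 = 0.67 |

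The residual variance of a single imputed value falls by 21% to 33%. That is not yet an effect on a reported result.

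**Step 3: effect on the treatment comparison.** For a normal outcome with fraction m missing, the variance is multiplied by R² + (1 − R²)/(1 − m). With 150 per arm, SE = 22 × √(2/150) = 2.540 mm and the complete-data half-width is 1.96 × 2.540 = 4.979 mm.

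Take correlations 0.6, 0.6, 0.4 (R² 0.36, then 0.432/0.84 = 0.514) and m = 20%:
- Day 3 only: 0.36 + 0.64/0.8 = 1.160; half-width 4.979 × √1.160 = 5.363 mm.
- Days 3 and 8: 0.514 + 0.486/0.8 = 1.121; half-width 5.273 mm.
- Gain: 0.090 mm.

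With adjacent-visit correlations from 0.4 to 0.75:

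| m | Half-width gain (mm) | Power gain (points) |
|---|---|---|
| 2% | 0.005–0.008 | about 0.1 |
| 5% | 0.012–0.020 | 0.2–0.3 |
| 10% | 0.025–0.041 | 0.3–0.5 |
| 20% | 0.055–0.090 | 0.7–1.3 |

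An imputation simulation (300 subjects, 8 centres as 0/1 indicators, data missing completely at random, correlations 0.6, 0.6, 0.4) agrees. The average SE, Day 3 only against Days 3 and 8, was 2.58 against 2.57 mm at 5% missing, 2.63 against 2.61 at 10%, and 2.76 against 2.71 at 20%. Neither model was biased there. If Day 8 is missing too, the gain is zero.

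**Step 4: bias when skipping depends on recovery.** Large-sample simulation with SD 22 mm, true difference 5 mm, the Step 2 correlations, and Day 5 missing with Day 8 seen in 5% to 20%, skipping being more likely the lower the Day 8 pain. The difference is 2.32% minus 1.16%, so a negative bias favours non-inferiority.
- Same mechanism in both arms, Day 3-only imputation: about −0.06 to −0.22 mm.
- Mechanism in the 2.32% arm only: about +0.4 to +1.6 mm.
- With Day 8 in the model: about zero in every case.

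The size depends on how steeply skipping rises with recovery. A repeat in which the log-odds of skipping rise by 1 for each SD of lower Day 8 pain gave ranges in line with these. Stronger assumed dependence reached about −0.5 mm in the first case and +2.7 mm in the second.

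**The case against.** The strongest reply is that little depends on this analysis. The primary per-protocol analysis has no imputation, and SAP 4.2.2 lists absence of a Day 5 POM among the possible reasons for exclusion from that population. Day 8 is not ignored elsewhere either: item 4 of SAP 4.5.1.3 imputes it, and Protocol 12.2.9 plans a repeated-measures model over Days 3, 5 and 8 without imputation. SAP 3.3 maps visits on Days 4 to 6 to Visit 3, so a late visit need not leave Day 5 missing. No document gives a rate of missed Visit 3 or says that early healers skip it. All of this stands, and it keeps the point small. It does not give a reason to leave Day 8 out of item 3.

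Two stronger readings are tempting and are not supported.

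- A reader might infer that the MCMC branch cannot handle centre, a nominal variable with at least 8 levels (300/40 = 7.5, rounded up). The documents do not show this. The SAP states no coding, defers details to another document, and its code is not visible. Centre is fully observed and can enter a joint-normal model as 0/1 indicators; 7 indicators worked in the Step 3 simulation. Leaving centre out altogether changed the average SE by less than 0.01 mm (assumed centre SD 5 mm).
- A reader might infer that 4.5.3 contradicts item 4. It does not. The Day 3 clause is limited to the Day 5 ANCOVA endpoint, and a separate imputation set for the repeated-measures model is compatible with it. What is missing is a statement of whether one run serves both.

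**Conclusion.** The concern holds in a narrow form. For the supportive ITT ANCOVA, SAP 4.5.3 leaves out Day 8 POM, a measured predictor, for subjects who miss Visit 3 and attend Visit 4. The precision cost is at most about 0.09 mm on a half-width of roughly 5.0 to 5.5 mm, against a 13 mm margin. The better reason to add Day 8 is bias: a few tenths of a millimetre or less if skipping follows recovery alike in both arms, and about 0.4 to 1.6 mm if it does so in one arm only, which is a stress case and less likely under blinding. These sizes rest on assumed correlations, missing rates and skipping mechanisms, none of which the documents give. Nobody should read this as a threat to the SAP's primary result. There is also no benefit for subjects who drop out before Day 5. It is a free improvement of low severity.

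**What to change.** State in SAP 4.5.3 that POM at Days 3, 5 and 8 is imputed jointly, with treatment, baseline POM and centre in the model. Centre should be declared as a class variable or as 0/1 indicators. Use a method valid for any missing pattern, for example fully conditional specification, so that the regression-or-MCMC branch is no longer needed. State also that the same 50 datasets feed items 3 and 4 of 4.5.1.3. The ANCOVA, the pooling step and the primary analysis stay as they are.

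The cost is a change to the imputation specification and its code, made before unblinding. No new data are needed.
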